Joslin Diabetes Center

Committee on Human Studies

Application for Review and Approval of Research and Training Projects Involving Human Research

Principal Investigator: [name] [name]

Co-Investigator(s): [name] NP, [name]

Project Title: Determining the Efficacy of Continuous Glucose Monitoring to Reduce Hypoglycemia and Improve Safety in Patients with Hypoglycemia after Gastric Surgery

Funding: Dexcom

Study Contact: [name] [name] [name]

1. PURPOSE OF PROTOCOL:

Obesity and related comorbidities, such as type 2 diabetes and cardiovascular disease, are increasingly recognized as major threats to individual and public health. Unfortunately, it is very difficult to achieve sustained weight loss with current medical approaches. Given these critical unmet needs, both clinicians and patients alike have embraced the results of recent controlled clinical trials demonstrating potent effects of bariatric surgical procedures to not only induce sustained weight loss but also to improve or normalize obesity-related comorbidities, including type 2 diabetes. Remarkably, surgery is superior to medical therapy for weight loss and diabetes, improves lifespan, and results in sustained improvement in glycemic control and reduced need for medications [1]. Such data have led to an explosion in the number of bariatric surgeries performed in the US – now over 200,000 annually [2]. While benefits of bariatric surgery are achieved with low operative mortality [3], longer-term intestinal and nutritional complications can occur.

One particularly challenging and sometimes severe complication of bariatric and other forms of gastric surgery (e.g. roux-en-Y gastric bypass, sleeve gastrectomy, gastrectomy for ulcer, fundoplication for reflux esophagitis) is hyperinsulinemic hypoglycemia [4]. While most commonly reported with roux-en-Y gastric bypass, hypoglycemia has also been observed with sleeve gastrectomy, a procedure increasingly employed in the US [5]. Prevalence estimates vary according to method of ascertainment, ranging from symptoms in 30% of patients to hospitalization required in <1%. However, studies utilizing continuous glucose monitoring suggest substantial hypoglycemia occurs even in completely asymptomatic patients post-RYGB, ranging from 29 to 71 min/day of sensor glucose values <60 mg/dL. In one study, 75% of 40

Approved by
JDC/CHS

Metabolic studies in patients with post-gastric surgery hypoglycemia reveal profound alterations in glycemic and hormonal patterns in the postprandial state occurring with altered gastric anatomy [8]. Plasma insulin concentrations are inappropriately high at the time of hypoglycemia, indicating dysregulation of insulin secretion as an important mechanism [9]. While initial reports demonstrated pancreatic islet hypertrophy, pancreatic resection does not cure hypoglycemia [4] [10, 11], and excessive islet number has not been observed in all series [4] [10, 12-14]. One candidate mediator of increased insulin secretion is GLP-1, an incretin peptide released from intestinal L-cells in response to meals, in turn stimulating insulin secretion in a glucose-dependent manner. Indeed, postprandial levels of GLP-1 are increased by >10-fold in post-bypass patients, are even higher in those with hypoglycemia, and correlate inversely with postprandial glucose levels [9, 15]. Furthermore, short-term pharmacologic blockade of the GLP-1 receptor markedly attenuates insulin secretion in post-bypass individuals [16], but increases GLP-1 levels in some studies [17, 18]. Interestingly, plasma levels of counterregulatory hormones such as cortisol and glucagon do not differ in the postprandial state in patients with symptomatic vs. asymptomatic hypoglycemia [9], but counterregulatory hormones are reduced during sustained hypoglycemia (hypoglycemic clamp) [19]. Additional gastrointestinal factors which could modify systemic metabolism include dietary composition, gut microbiota [20], bile acid composition [21], and intestinal adaptive responses [22]; these may influence absorption of glucose and other nutrients, intestinally-derived hormonal responses, and the magnitude of CNS-gut-liver regulatory loops. Finally, genetic variation could also contribute to altered hormonal responses and sensitivity [23].

Approved by
JDC/CHS 

A cornerstone of therapy is dietary modification, aimed at reducing intake of high glycemic index carbohydrates [24]. Both diet and pre-meal acarbose [25] aim to minimize rapid postprandial surges in glucose which are triggers for glucose-dependent insulin secretion. Additional therapies include octreotide (to reduce incretin and insulin secretion) [26], diazoxide (to reduce insulin secretion) [27], calcium channel blockade (to reduce insulin secretion) [28], gastric restriction or banding (to slow gastric emptying) [29], and providing nutrition solely through a gastrostomy tube placed into the bypassed duodenum [30]. Surprisingly, reversal of gastric bypass is not uniformly successful [4] [10, 11], suggesting the importance of underlying genetics and/or compensatory mechanisms which persist after surgical reversal. Finally, while pancreatic resection was initially employed for patients with life-threatening hypoglycemia [4], this procedure is not uniformly successful in remitting hypoglycemia and thus is not routinely considered at the present time.

Despite strict adherence to medical nutrition therapy and clinical use of multiple medical options above, usually in combination, some patients continue to have frequent hypoglycemia. While hypoglycemia most commonly occurs in the postprandial state, it can also be observed in response to increased activity and emotional stress. Importantly, patient safety is additionally compromised when hypoglycemia unawareness develops with recurrent hypoglycemia. Patients are often disabled by hypoglycemia which occurs multiple times per day, leading to inability to drive or maintain employment, and causing fear of eating and exercise due to potential provocation of hypoglycemic events, cardiac arrhythmias [31], syncope, falls, and seizures. Thus, there is an urgent need for improved approaches to the prevention and treatment of severe hypoglycemia to maintain health, allow optimal nutrition, and improve safety in individuals with PBH.

In our extensive clinical experience caring for patients with hypoglycemia after gastric surgery, we have observed that personal (unmasked) continuous glucose monitoring can improve patient safety and reduce hypoglycemia. CGM alarms, both glucose threshold and rate of change alarms, can alert the patient to treat to raise glucose - before severe hypoglycemia occurs. This is particularly helpful for those patients with hypoglycemic unawareness, who develop neuroglycopenia without any warning symptoms [4]. In this context, and recognizing the lag between capillary and sensor glucose values, we advise patients to respond to the rate of change alarm, so that treatment can occur before neuroglycopenia develops.

This approach is also similar to our strategy in ongoing studies of patients with post-bariatric hypoglycemia, in which we are testing the ability of CGM used in conjunction with algorithm-based prediction of hypoglycemia to guide delivery of glucagon. While this approach is still under study, use of CGM to predict hypoglycemia in this context has again reinforced the potential utility of CGM alone to provide patients with real-time sensor glucose values and predictive alarms, allowing patients to detect imminent hypoglycemia and self-treat to prevent severe hypoglycemia and dangerous neuroglycopenia. Moreover, real-time glucose information will also provide patients with information about glucose responses to specific food types and quantity, potentially allowing them to better individualize dietary choices in order to prevent postprandial glycemic spikes associated with excessive insulin secretion and subsequent hypoglycemia.

In parallel with glucose measures, we will assess activity (using a FitBit Charge 2) to define the relationship between activity measures and hypoglycemia risk and begin to provide guidance for patients about predicted glycemic responses to activity.

Our studies will also provide crucial data to guide next-step studies aimed at testing whether chronic CGM use could also reverse hypoglycemia unawareness, further improving safety and quality of life for this patient population.

[figure not shown]
Approved by
JDC/CHS 

The clinical relevance of severe hypoglycemia with neuroglycopenia is undeniable, as patient safety, cognition, and quality of life can be compromised. Given the continued increase in bariatric surgery and continued need for other forms of gastric surgery, the population of patients with hypoglycemia is expected to increase further, making the proposed studies essential for consideration of this approach to achieving safety.

2. STUDY DESIGN:

[figure not shown]
The proposed study is designed to assess the efficacy of unmasked personal CGM to reduce the frequency of hypoglycemia after gastric surgery. Specifically, we will analyze glycemic patterns during unmasked CGM wear, in comparison to the baseline of masked CGM wear. Initially study participants wore Dexcom G4 Professional (Pro) CGM devices, but as of July 2020 this has changed to the Dexcom G6 Pro. The Dexcom G6 Pro is worn for 10 days masked and 10 days unmasked, as this is the life span of the G6 sensor / transmitter pairs which are single use. Please note that we have chosen to have a consistent masked monitoring first, as providing unmasked data to participants first could alter their dietary or other patterns and reduce ability of the study to independently assess efficacy of the CGM intervention.

Figure 2. Overview of Research Plan Through June 2020 (Dexcom G4 Pro)

Approved by
JDC/CHS 

Figure 3. Overview of Research Plan July 2020 Onward (Dexcom G6 Pro)

Visit 1:

Screening: We will recruit adult male or female patients with history of severe hypoglycemia after gastric surgery, defined as (1) symptoms of hypoglycemia with glucose <55 mg/dL [32] and resolution by glucose or food ingestion, (2) neuroglycopenia or (3) hypoglycemia requiring assistance of others. Potential participants will be identified from the hypoglycemia clinic at Joslin (directed by [name]). The study consent form will be reviewed in detail with potential participants, and patients consenting to participation will be asked to sign the IRB-approved consent form. Patients will undergo a history and physical examination, with particular emphasis on inclusion and exclusion criteria. Blood and urine samples will be obtained for screening laboratory testing including hemoglobin A1c, CBC, comprehensive chemistry, urinalysis, and pregnancy test (if applicable).

Participants will complete the following surveys:

- 1) HFS-II survey to assess fear of hypoglycemia and its impact on their daily routine Questions focused on insulin use will be omitted as participants do not have diabetes. (The modified survey has also been previously utilized for patients with hypoglycemia.)
- 2) The modified Clarke's hypoglycemia awareness questionnaire [33, 34] will be administered to all participants; score of ≥ 4 implies impaired awareness of hypoglycemia.
- 3) Edinburgh Hypoglycemia Scale to measure the intensity of hypoglycemic symptoms on a 7 point scale
- 4) Dumping Symptom Rating Scale to measure the severity and frequency of 9 different dumping symptoms.

CGM sensor placement and instruction: a continuous glucose monitor sensor and transmitter (Dexcom G4 or Dexcom G6) will be placed on the anterior abdominal wall. The CGM will be set to blinded mode. Participants will be provided a glucometer and instructed in sensor insertion, glucometer measurement of capillary glucose, and calibration techniques. Participants will be provided with and instructed in completion of a detailed log to record symptoms experienced, capillary glucose level and action taken (e.g. food, glucose type and quantity used, effectiveness), activity, and all food intake. The HypoMap tool may be utilized in parallel if the participant has access to a smart phone. Participants will be asked to email logs (identified with study acrostic only) on a daily basis to study staff.

Participants will be provided with a spare sensor in case the primary sensor is dislodged.

Approved by
JDC/CHS

Participants will be provided with a fitness tracker (FitBit Charge 2) to be worn throughout the duration of the continuous glucose monitoring, and will be instructed in its use (4 weeks for participants wearing the Dexcom G4 Pro and 20 days for participants wearing the Dexcom G6 Pro). This device will be used to assess activity level of each participant and to assess relationships between the timing of activity and hypoglycemia. This device will be returned at the end of the study.

Visit 2:

For participants wearing the Dexcom G6 Pro, insertion of second sensor: this visit will occur 10 days after visit 1. All other aspects of this visit are the same as were in place for participants wearing the Dexcom G4 Pro. Study staff will remove the sensor, and review participant diaries. A new sensor will be inserted. The study CGM will be unmasked, and alarms will be set for (1) sensor glucose <70 mg/dL, and (2) trend alarm for glucose drop of >3 mg/dL/min. Participants will be instructed in the meaning of alarms and suggested responses to alarms. Participants will be provided logs identical to those for visit 1, except that participants will also be asked to record alarms and action taken in response to alarms. The modified Clarke's hypoglycemia awareness questionnaire [33, 34] again will be administered to all participants.

Visit 3:

Return of study materials and removal of the 2nd sensor: this visit will occur 10 days after visit 2. Study staff will remove the sensor, download the sensor, and review logbooks to ensure data collection. Activity trackers will be returned to study staff. The modified Clarke's hypoglycemia awareness questionnaire [33, 34] will be administered. Frequency of hypoglycemia will be reviewed, and any recommendations for dietary or medication adjustments will be reviewed with the participant by the study physician.

Hardware Cleaning:

Dexcom G6 sensors and transmitters are single use and are worn only once per 10 day period by one participant.

3. INCLUSION / EXCLUSION CRITERIA

Inclusion Criteria

1. Males or females diagnosed with ongoing post-bariatric or post-gastric surgery hypoglycemia with prior episodes of neuroglycopenia
2. Age 18-65 years of age, inclusive, at screening.
3. Willingness to provide informed consent and follow all study procedures, including attending all scheduled visits.

Exclusion Criteria

1. Documented hypoglycemia occurring in the fasting state (> 12 hours fast);
2. Chronic kidney disease stage 4 or 5 (including end-stage renal disease);
3. Hepatic disease, including serum ALT or AST greater than or equal to 3 times the upper limit of normal; hepatic synthetic insufficiency as defined as serum albumin < 3.0 g/dL; or serum bilirubin > 2.0;
4. Congestive heart failure, NYHA class II, III or IV;
5. History of myocardial infarction, unstable angina or revascularization within the past 6 months or 2 or more risk factors for coronary artery disease including diabetes, uncontrolled hypertension, uncontrolled hyperlipidemia, and active tobacco use.
6. History of syncope (unrelated to hypoglycemia) or diagnosed cardiac arrhythmia
7. Concurrent administration of β -blocker therapy;

Approved by
JDC/CHS 

8. History of a cerebrovascular accident;
9. Seizure disorder (other than with suspect or documented hypoglycemia);
10. Active treatment with any diabetes medications except for acarbose;
11. Active treatment with octreotide or diazoxide;
12. Active malignancy, except basal cell or squamous cell skin cancers;
13. Personal or family history of pheochromocytoma or disorder with increased risk of pheochromocytoma (MEN 2, neurofibromatosis, or Von Hippel-Lindau disease);
14. Known insulinoma;
15. Major surgical operation within 30 days prior to screening;
16. Hematocrit < 33%;
17. Bleeding disorder, treatment with warfarin, or platelet count <50,000;
18. Blood donation (1 pint of whole blood) within the past 2 months;
19. Active alcohol abuse or substance abuse;
20. Current administration of oral or parenteral corticosteroids;
21. Pregnancy and/ or lactation: For women of childbearing potential: there is a requirement for a negative urine pregnancy test and for agreement to use contraception during the study and for at least 1 month after participating in the study. Acceptable contraception includes birth control pill / patch / vaginal ring, Depo-Provera, Norplant, an IUD, the double barrier method (the woman uses a diaphragm and spermicide and the man uses a condom), or abstinence.
22. Use of an investigational drug within 30 days prior to screening.
23. Not having a smart phone compatible with the Dexcom G6 Pro CGM (in order to receive / view glucose data).

4. DATA ANALYSIS / SUBJECT SELECTION

Statistical and Analytical Plan

All participants who have consented to the study and completed at least one monitoring period of CGM use will be included in the data analysis set. Adverse events, vital signs, physical examination, and laboratory safety variables (Screening to Final Visit) will be reviewed and summarized on an ongoing basis during the study to evaluate safety. Safety data will be presented in tabular and/or graphical format and summarized descriptively, where appropriate.

Data will be stored using a secure, web-based application designed to support data capture for research studies (RedCap), providing: 1) an intuitive interface for validated data entry; 2) audit trails for tracking data manipulation and export procedures; 3) automated export procedures for seamless data downloads to common statistical packages; and 4) procedures for importing data from external sources. Data are stored and are backed up on a scheduled basis with data encryption for any regulated data types (private health data (PHI) which require backup media in an encrypted format. Data will be maintained in protected files at Joslin Diabetes Center. Only deidentified data will be transferred (via secure electronic file transfer) between collaborators.

CGM data, alarms, reported symptoms, need for assistance, hypoglycemia awareness scale, and timing of symptoms relative to sensor glucose levels will be recorded. We will also define CGM values, both during the day and night, using thresholds <55 (severe hypoglycemia)[32], 55-70 (moderate hypoglycemia), 70-180 (euglycemia), and >180 mg/dl (hyperglycemia).

CGM data will be analyzed in several ways: (1) minutes per day <70 mg/dl (primary analysis), (2) minutes per day <55 mg/dl, (3) number of episodes requiring assistance, (4) episodes of severe hypoglycemia (<55 mg/dl), (5) episodes of moderate hypoglycemia (55-70 mg/dl), and episodes of hyperglycemia (>180 mg/dl). In secondary analysis, data from days and nights (11 PM – 6 AM) will be analyzed separately. Activity measures, including total step number as well as duration of activity as defined by heart rate increment, will be analyzed to determine relationship to changes in sensor

Approved by
JDC/CHS 

glucose levels (Fitabase). For all data, paired analysis will be used to compare responses per participant for masked vs. unmasked periods.

Analyses will utilize either parametric (paired t tests) or non-parametric statistical tests (Wilcoxon signed-rank test), depending on data distribution for continuous variables, and chi square for categorical variables.

Sample Size and Justification

Approximately 40 subjects may be screened for this study, assuming approximately 30% will not meet inclusion criteria. To allow for potential drop-outs (assuming 20%), 28 subjects will be enrolled with goal for 20 subjects to complete all study visits.

Prior data from our group in patients with symptomatic post-bypass hypoglycemia (n=10, unselected for severity) demonstrate mean \pm standard error of 63 ± 23 minutes/day for sensor glucose <70 [4]. This was a small cohort, (n=10), was unselected for severity, and utilized an early Medtronic diagnostic CGM system. The cohort proposed in this study is expected to have longer duration of hypoglycemia daily. However, we have used these data to estimate power for the current study. We estimate power of 98% to detect a 50% reduction (32 minutes) in time <70 with alpha 0.05 (2-sided) for paired comparison of masked and unmasked monitoring periods with a sample size of 20. As noted above, we expect power will be higher due to increased severity in this sample cohort; even with the conservative calculations, we should have adequate power (0.8) to detect differences between masked and unmasked periods as low as 23 minutes per 24 hours.

Data will be analyzed after 10 individuals have completed the paired analysis of response to masked vs. unmasked CGM analysis. At that time, power will be reassessed, and sample size will be adjusted if needed.

Local Interim Data Analysis/Data Monitoring Plan

Data will be stored using a secure, web-based application designed to support data capture for research studies (such as RedCap), providing: 1) an intuitive interface for validated data entry; 2) audit trails for tracking data manipulation and export procedures; 3) automated export procedures for seamless data downloads to common statistical packages; and 4) procedures for importing data from external sources. Data are stored and are backed up on a scheduled basis with data encryption for any regulated data types (private health data (PHI) which require backup media in an encrypted format.

Data will be maintained in protected files at Joslin Diabetes Center. Only deidentified data will be transferred (via secure electronic file transfer) between collaborators.

Data Safety Monitoring Plan: The PI will be responsible for ensuring that recruitment and phenotypic analyses are conducted in accordance with the IRB- approved protocol and will review all adverse events and serious adverse events. The Joslin study coordinator will also perform a periodic review of all data from phenotypic analyses. The members of the study team will conduct regularly scheduled meeting approximately weekly as well as on an as-needed basis to review status of the trial inclusive of enrollment, oversight of informed consent, general conduct of the trial as well as reporting of any complications as needed to the NIH and IRB.

5. POSSIBLE BENEFITS:

The purpose of this study is to evaluate the efficacy of continuous glucose monitoring at reducing episodes of hypoglycemia in patients who experience hypoglycemia after gastric surgery. This project is not designed to be of direct benefit to any individual subject, although it is hoped that through the knowledge gained from these studies there will be general benefit to persons with or at risk of development of hypoglycemia following gastric surgery. Subjects enrolled in this study receive

Approved by
JDC/CHS 

comprehensive medical evaluation. As such, risks are appropriate in relation to the potential significant benefits for the large number of persons with or at risk for hypoglycemia after bariatric surgery. Thus, the potential benefits to society are likely to outweigh the risks to the individual subject.

6. POSSIBLE RISKS:

Risk of Device Reuse: This risk has been eliminated from this protocol as Dexcom sensors, transmitters and receivers will be used only by a single participant and thus do not require sterilization. Glucometers will not be cleaned or reused by subjects. A new meter will be given to each new participant.

Sensor inaccuracy:

Participants wearing the Dexcom G6 Pro CGM may take up to 1000 mg of acetaminophen every 6 hours (4 grams per 24 hours), without affecting sensor accuracy.

Sensor placement may cause bleeding, infection, clot formation (all minimal risk), bruising, or discomfort.

Phlebotomy may cause blood loss and discomfort. The total volume of blood sampling is approximately 15 ml for the screening visit. This should not pose significant stress to any individual. Volunteers will be requested not to donate blood within 2 months of the study. Any subject who has just donated blood will be asked to postpone entry into the study until 2 months have elapsed.

Screening Tests and Procedures: It is possible that as a result of the screening process a subject may learn that they have a health disorder that they were unaware they had. Every effort will be made to help the participant obtain the care that they need.

Breach of Confidentiality: While every effort will be made to protect the confidentiality of participant identifiable information, there is the potential loss of confidentiality by participating in this study.

Inconvenience and Unknown Risks: Participants may be inconvenienced by the time commitment involved in participation in the study. There may be other risks from this study not yet identified.

Participants can choose not to participate in the clinical research project and can withdraw consent at any time.

7. CONSENT PROCEDURES:

Subjects will be recruited from the Joslin Hypoglycemia Clinic. The study will be explained to the potential subject initially in the clinical setting or during a subsequent telephone screening session. The informed consent process will be inclusive of various types of education and counseling opportunities including an in-person or telephone screening, allowing for general overview of the procedures as well as options available for all subjects expressing interest in participation.

Those still interested after in person or telephone screening will be scheduled for screening visit(s) at the clinical research unit. The consent process will involve initial discussion of the purpose and scope of the research as well as risks and benefits. Ample opportunity will be provided for participants to read consent, share with family or other health care providers as well as have all questions answered by the Principal Investigator or their designated study staff prior to obtaining written informed consent using IRB approved documents. The consent form will include a description of risks and benefits, alternative

Approved by
JDC/CHS 

possible procedures, the availability of the investigating physicians throughout any study to discuss any concerns, the availability of the IRB to the patient throughout any study to discuss any concerns, and the fact that the patient can withdraw from the study at any time with no change in his/her standard treatment. There can be no changes in the protocol without the prior agreement of the IRB.

If the patient consents to enroll in the study, and the consent form is signed, further evaluation in the form of the medical and screening visit will take place to determine eligibility. One copy of the consent form will be retained by the principal investigator and one copy will be provided to the subject.

8. RECRUITMENT / SOURCE OF SUBJECTS:

Patients with post-gastric surgery hypoglycemia will be recruited for this study from the weekly Hypoglycemia Clinic at Joslin Diabetes Center, directed by [name]. Post-gastric surgery hypoglycemia syndrome is the most common diagnosis within this clinic. More than 200 patients with this syndrome have been evaluated to date at Joslin, and over 50 patients have participated in research studies to date. Recruitment will be performed in the Hypoglycemia Clinic by the research fellow or study coordinator.

9. RIGHTS AND PRIVACY:

Storage of private health information is solely in locked offices or on secure access protected computer sites and portable devices that may be used for patient data are encrypted to protect privacy. All study staff are trained in privacy protection and the ethical conduct of clinical research. Records will be made available for inspection by the safety officer upon request.

Please answer the following questions:

- Will medical history/clinical information be obtained from the subjects' medical records for the purpose of this study? If yes, please list what information will be recorded.
v YES NO
 - Age, gender, race
 - Date of surgery
 - Type of procedure
 - Pre-surgical BMI
 - Concomitant medical problems
 - Active and historical medications
 - History of hypoglycemia: first onset, symptoms, prior diagnostic testing and treatment approaches
- Will information resulting from this study (i.e. results of clinical/research lab tests, etc...) become part of the subjects' medical record or provided to the subject and/or others for clinical purposes? If, no, please list what information will not be given to the subject or recorded in their medical record and why.

Approved by
JDC/CHS 

YES NO

- Will subjects' identifiable health information* be shared with others outside of Joslin Diabetes Center? If yes, list whom this information will be shared with (please be specific, include names of collaborators, study sponsor contacts)?

YES NO

10. OMIT PROCEDURES / LEAVE STUDY:

We will inform patients that they may discontinue the study at any time without consequence.
They will be informed that their decision will not affect how they are treated.

11. INCENTIVES / REMUNERATION:

Participants will be given a payment of \$200.00 (provided as check) upon the completion of five study visits. The study will also compensate participants for the cost of parking or taxi services up to \$50 for each of the study visits.

Parking will be paid by vouchers on the participants are asked to come in for a study visit.

For participants wearing the Dexcom G6 Pro, as the sensors and transmitters are single use only, they cannot be kept and used again. Also, as a personal receiver is not needed for the Dexcom G6 Pro, a Dexcom G6 receiver is not provided to the participant.

Participants will not be able to keep the FitBit; it will be returned to study staff at the end of the study.

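### Does leaving the choice between paired t and Wilcoxon to the data distribution make the primary result ambiguous?

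*Combined protocol and SAP*

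**What the plan says.** All the relevant text is in section 4 (Data Analysis / Subject Selection).

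- **Endpoint.** The Statistical and Analytical Plan lists "minutes per day <70 mg/dl (primary analysis") first among the CGM measures.
- **Contrast.** "paired analysis will be used to compare responses per participant for masked vs. unmasked periods".
- **Test.** "Analyses will utilize either parametric (paired t tests) or non-parametric statistical tests (Wilcoxon signed-rank test), depending on data distribution for continuous variables".
- **Sizing.** Sample Size and Justification takes pilot data on 10 patients, with mean and "standard error of 63 ± 23 minutes/day for sensor glucose <70", and states: "We estimate power of 98% to detect a 50% reduction (32 minutes) in time <70", at two-sided alpha 0.05 with 20 pairs. It adds power of 0.8 at 23 minutes.
- **Look at 10.** "Data will be analyzed after 10 individuals have completed the paired analysis of response to masked vs. unmasked CGM analysis"; power is then reassessed and the sample size adjusted if needed.

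The plan does not say how the distribution is judged, on which quantity, or when. It does not name the estimate and confidence interval that accompany the test.

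**The concern.** The two tests do not target the same quantity. The paired t test concerns the mean difference, which is the scale of the 32-minute sizing figure. The estimate that usually accompanies Wilcoxon is the Hodges-Lehmann pseudo-median, which is lower than the mean when differences are right-skewed.

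Skewed period values are foreseeable. The pilot SD exceeds the pilot mean, and minutes per day cannot be negative. So a true halving of mean time below 70 could be reported as a smaller number purely because of the branch taken. The test used at 10 completers could also differ from the one used at 20. At stake would be the meaning of the headline estimate and, if the choice were made after seeing p-values, the type I error.

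**Working it through.** **Inputs from the plan.** Pilot mean 63, SE 23, n = 10; 20 pairs; two-sided alpha 0.05; 50% reduction.

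- SD = 23 × √10 = 72.7; CV = 72.7 / 63 = 1.15.
- A normal distribution with these values would put Φ(−63 / 72.7) = Φ(−0.87), about 19%, below zero. The period values are therefore unlikely to be normal.
- Target mean difference = 0.5 × 63 = 31.5, stated as 32.

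**The plan's power figures.** The SD of the paired differences is not given. If every participant's value is exactly halved, it is 72.7 / 2 = 36.4. By normal approximation, power = Φ(δ√20 / 36.4 − 1.96):

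- δ = 32: Φ(3.93 − 1.96) = 97.6%
- δ = 23: Φ(2.83 − 1.96) = 80.7%

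Both are close to the stated 98% and 80%. The noncentral t gives 96.2% and 76.5%. The figures are thus reachable, but only with an input that the plan leaves unstated. That is a separate matter from the choice of test.

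**Population mean against pseudo-median for a 50% reduction.** The mean is 31.5 in every model. The pseudo-median depends on an assumed shape:

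| Assumption | Pseudo-median (min/day) |
|---|---|
| Lognormal or gamma pairs, raw correlation 0.30-0.91 | 21.8-23.4 |
| Exact halving in each person (SD of differences 36.4) | 24.5-24.9 |
| Right-skewed differences, SD 33-37 as the power statements imply | about 24-26 |
| Symmetric differences, or a constant shift | about 31.5 |

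The distance from 31.5 is therefore between 0 and about 10 min/day, according to assumptions that the plan does not supply.

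**What each branch would report.** The table compares two parameters of one distribution. It does not describe the plan's procedure, in which the t test is used only when the observed differences look normal. Assumed rule: Shapiro-Wilk at 5% on the 20 differences. Models: lognormal and gamma margins, mean 63, SD 72.7, latent correlation 0.4 to 0.93, 4,000 simulated trials per setting. Average reported values:

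| Margins | t branch (mean) | Wilcoxon branch (Hodges-Lehmann) | Gap |
|---|---|---|---|
| Lognormal | about 24-26 | about 22.5-24 | about 1-2.5 |
| Gamma | about 26-30 | about 22-24 | about 4-6 |

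The t branch is taken in about 9-39% of trials, mostly those in which no extreme difference was drawn. Its mean then lies nearer to the pseudo-median.

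**Power and type I error**, rule against always-Wilcoxon, at latent correlation 0.4 / 0.6 / 0.8:

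- Lognormal: 0.74 / 0.88 / 0.99 against 0.76 / 0.89 / 0.99.
- Gamma: 0.53 / 0.68 / 0.92 against 0.53 / 0.68 / 0.92.
- Type I error of the rule: 4.3-5.1%. Even an analyst who took the smaller of the two p-values would reach only 5.6-5.9%.

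**The look at 10.** Under the same assumed rule, the test chosen on the first 10 pairs differs from that chosen on all 20 in about 20-38% of trials, depending on the model. The stated purpose of the look is to reassess power and sample size. The plan attaches no efficacy claim or stopping rule to it, so no stated decision turns on which test is used there.

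**The case for a change.** The strongest case for a change is that the gap is real and cheap to close. A sentence or two would name one test, its estimate and its interval, and apply them at both analyses. Without that, readers cannot know beforehand whether the headline is a mean or a pseudo-median. Judging masked-period values instead of differences would change the chosen test in 9-34% of simulated trials. Paired t and Wilcoxon disagree at p < 0.05 in up to about one trial in six when the within-person correlation is low. And under skewness both branches report, on average, less than the 32 minutes for which the trial was sized.

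The omissions stand as described. The consequences do not go far:

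- Most of the disagreement in p-values arises where the data are plainly skewed and the paired t test loses power. A distribution-based choice then usually selects Wilcoxon, so the rule's power follows Wilcoxon's.
- The 32 minutes is a sizing figure. The plan does not make it a threshold for success, and nothing prevents the mean difference from being reported beside either test.
- Both tests operate on paired differences, so a competent analyst would check the differences. The variable and the paired contrast are named; only the summary measure is missing.

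**Conclusion.** No change follows. The plan leaves a minor detail unwritten, and ordinary practice supplies it: examine the paired differences, choose between two named and defensible tests, and report an estimate with its interval.

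The effect is small. Power is within about 0.02 of Wilcoxon's, type I error is close to 5%, and the average gap between what the two branches would report is about 1-6 min/day, or none if the differences are symmetric. The larger contrast, 31.5 against about 22-26 min/day, compares always using the mean with always using the pseudo-median, and it needs right-skewed differences.

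These sizes rest on a Shapiro-Wilk rule, lognormal or gamma margins, a proportional reduction and a range of correlations. All are assumed; the plan gives only a pilot mean, a standard error and a target reduction. Naming one test in advance would be tidier, but the conclusion from the plan as written would be sound.
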